9.6.2. Description of comparator(s)

Participants randomised to the control group will receive TAU only. It is anticipated that participants receiving TAU will have been prescribed antidepressant medication(s) by their GP and/or have been referred to local IAPT or other psychological therapy services. Usual care for insomnia is likely to be general sleep advice, hypnotics, or sedative antidepressants. We will record TAU in both trial arms.

9.7. Baseline Assessments

The researcher will answer any questions that participants may have, remind them that that they are free to withdraw from the study at any point and obtain written or remote informed consent (depending on whether baseline is in person or remotely). The baseline meeting will take place at a location most convenient for the participant and may include, for example, general practice or participant home. If inperson meeting is not possible the research team can hold the baseline appointment remotely over Teams and collect remote informed consent. An electronic case report form (e-CRF) will be used to record information for each participant. Should the researcher be unable to access the e-CRF on the computer, a paper copy of the CRF may be used and data entered by researcher into the trial database at the earliest convenience.

The researcher will collect basic demographic data, medication/comorbidity data, and ask participants to complete self-report questionnaires (related to sleep, depressive symptoms, and functioning; see Table 7 below) and computerised tasks that examine emotional processing bias [Facial Expression Recognition Task (FERT; 17), Emotional Categorisation Task (ECAT; 17), and Emotional Recall Task (EREC; 17) from the Oxford Emotional Test Battery].

Briefly, the Oxford Emotional Test Battery is a computerised assessment of cognitive-emotional processing, which has shown sensitivity to depression and its pharmacological and behavioural treatment. The following 3 tasks will be administered (see appendix E for examples):

- FERT: faces with six different basic emotions (happiness, fear, anger, disgust, sadness, surprise) are displayed on a screen and participants are asked to identify the emotion in each face as quickly and accurately as possible by selecting a corresponding button. The task takes approximately 15 minutes to complete (5 minutes per block). The primary FERT outcomes are accuracy for sad and happy facial expressions, defined as the percentage of accurately identified faces for each emotion (Number of correct responses for each emotion)/(Number of faces of each emotion).
- ECAT: the ECAT assesses speed to respond to positive and negative self-referent personality descriptors. Participants are asked whether they would 'like' or 'dislike' to be referred to as each characteristic. The task takes approximately 5 minutes to complete. Mean reaction time for correct responses for positive and negative words will be considered as the main outcomes for this task. THE ECAT also serves as the stimulus set for the subsequent free recall (see EREC below).
- EREC: Participants are asked to write down (type) as many of the words previously presented in the emotional categorisation task (ECAT), in a 2-minute interval. The recall of emotional words gives a measure of bias for both positive and negative words. The main outcome measures are number of positive and negative self-referent words correctly recalled.

Participants will be provided with an actigraph watch (a device which measures movement to infer sleep/wake periods and environmental light exposure) and instructions on its use. The researcher will review instructions with the participant to ensure they are clear on its use and ask them to wear the watch for the next seven days. Concurrently, participants will record a modified daily sleep diary (CSD; 25) for seven days to capture nightly subjective sleep and daytime activation. On completion, participants will return the diary and watch through either 1) recorded-delivery postage; 2) direct delivery to the researcher's office or local practice; or 3) arrange for the researcher to collect directly from the participant.

On return of sleep diary and actigraph watch, participants will be randomised by a member of the research team to either SRT+TAU or standalone TAU. The SRT+TAU group will meet with the trained nurse on six occasions over approximately an eight-week period to receive guidance on the rationale and implementation of SRT (see *Interventions* below).

Questionnaires will be collected electronically unless the server is unavailable or a participant requests to complete the questionnaire in paper form. Tasks will be completed on a study laptop if held in person, or completed online using the participant's device (e.g., laptop, desktop, or tablet) if the visit is completed remotely.

Table 7: Data c	collection at	baseline visit
-----------------	---------------	----------------

1.	Demographic and clinical information	Post code*, sex, age, marital status, level of education, ethnicity, self-reported height and weight (BMI), number of episodes of depression, age of onset of first depression episode, antidepressant treatment (type/dose) and duration, psychological therapy for depression, insomnia duration, insomnia treatment, medical conditions (records)
2.	Self-report questionnaires (assessing depression, insomnia, level of activation, affect, repetitive thinking, wellbeing, cognitive complaints)	Patient Health Questionnaire-9 (PHQ-9; 18), Insomnia Severity Index (ISI; 19), Behavioural Activation Scale for Depression – Short Form (BADS-SF; 20), Positive and Negative Affect Schedule (PANAS; 21), Perseverative Thinking Questionnaire (PTQ; 22), Warwick-Edinburgh Mental Wellbeing Scale (WEMWBS; 23); British Columbia Cognitive Complaints Inventory (BC-CCI; 24)
3.	Oxford Emotional Test Battery	FERT; ECAT; EREC
4.	Subjective sleep and daytime activation	Adapted sleep diary (CSD; 25) completed daily for 1 week – providing information on sleep timing, continuity, and quality, and daytime activation (4 items from the BADS-SF [20])
5.	Objective estimates of sleep	Actigraph watch (MotionWatch 8, CamNTech Ltd.) worn for 1 week – providing information on objective estimates of sleep timing and continuity, daytime activity and light exposure
6.	Adverse events	Adverse effects [pre-defined as accidents, falls, and near misses while driving, and suicidal ideation (item 9 from PHQ9)]
	be converted to an index of multiple nted by group at baseline for descri	e deprivation score and the demographic variables will be ptive purposes only.

9.8. Subsequent Assessments

Following the baseline assessment, participants will have follow-up assessments at 4-, 8-, and 26-weeks post-randomisation. The window of opportunity for participants to complete assessments at each timepoint will be as follows: 4 weeks (+14 days), 8 weeks (+28 days), 26 weeks (+28 days). For each follow-up, a member of the research team will notify participants (through e.g., call, text, email or letter) that their assessment is due (see Table 8 for breakdown of outcomes collected at each time-point).

Depending on participant preference (which will be ascertained at baseline), and to optimise retention, questionnaire outcome measures can be completed electronically through web-based survey (participants will be sent the link to access), over the phone with the research team, or using a paper version. Should participants want to complete questionnaire outcomes over the phone, we will ensure that the researcher is blind to group allocation. A sleep diary and actigraph watch will be posted to all participants (at 8 weeks and 26 weeks) along with a pre-paid return envelope for sending back to research team. Computer tasks (i.e. FERT, ECAT, and EREC) at 8 and 26 weeks can be completed remotely by the participant at home, over the internet (using the e-Pro system). If the participant does not have access to their own device or prefers

Clinical Research Protocol Template version 15.0

© Copyright: The University of Oxford and Oxford University Hospitals NHS Foundation Trust 2019

to complete the tasks in person with the researcher present, they may complete the task with a researcher at a convenient location (e.g. GP practice, home).

A description of the primary and secondary outcomes for the trial are listed below. Table 8 details what outcomes are assessed at the follow-up assessment points.

Primary clinical outcome: The primary outcome is self-reported depression severity at 26 weeks postrandomisation measured with the PHQ-9. The PHQ-9 is a nine-item (0-27 score) measure of depressive symptoms that is widely used in primary care mental health and is sensitive to change (26). A cut-off score \geq 10 shows good sensitivity and specificity for major depression, while a >20% reduction in score is suggested to be the minimal clinically important difference (27). The PHQ-9 will also be completed by participants at mid-treatment (i.e. 4-weeks post-randomisation) and post-treatment (8-weeks postrandomisation).

Secondary mechanistic outcomes:

- Objective estimates of sleep and circadian rest-activity rhythms: measured using actigraphy (Motionwatch 8, Camntech Ltd.) over 7 days to derive estimates of sleep continuity, as well as non-parametric circadian rhythm metrics of relative amplitude (RA) and interdaily stability (IS) of rest-activity.
- Emotional processing bias: Facial Expression Recognition Task [FERT] for the perception of social cues and the Emotional Categorisation Task [ECAT] and Emotional Recall Task [EREC] for memory of affective word stimuli [from the Oxford Emotional Test Battery (17, 28)] (See appendix E for examples)
- Positive and negative affect: Positive and Negative Affect Schedule (PANAS; one-week version; (21))
- Repetitive negative thinking: Perseverative Thinking Questionnaire (PTQ; 22)
- Behavioural activation: Behavioural activation for depression scale-Short

Form (BADS-SF; 20)

Secondary clinical outcomes:

- Insomnia severity assessed with the insomnia severity index (ISI; 19)
- Self-reported sleep and daytime activity assessed prospectively: consensus sleep diary (CSD; 25)
- Psychological well-being: Warwick-Edinburgh Mental Wellbeing Scale (WEMWBS (23))
- Cognitive complaints: British Columbia Cognitive Complaints Inventory (BC-CCI (24))
- Secondary safety outcomes:
- Adverse events: Falls, accidents (road-traffic and work-related), near-miss driving incidents, and falling asleep while driving; and suicidal ideation (item 9 from the PHQ9).

Tertiary (exploratory) outcome:

• Daytime activity levels and patterning of light exposure: derived from wrist-worn actigraphy

Collection time-point	Measure
4-weeks (+14-day window) post-randomisation	 Questionnaires: PHQ-9; ISI; BADS-SF; adverse events
8-weeks (+28-day window) post- randomisation	Questionnaires: PHQ-9; ISI; PANAS; PTQ; BADS- SF; WEMWBS; BC-CCI; adverse event questionnaire
	Computerised tasks: FERT; ECAT; EREC
	Sleep and daytime activity diary (CSD)
	Actigraphy (7 days)

Table 8: Data collection at 4-, 8-, and 26- weeks post-intervention

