Secondary	Mediation hypothesis: To examine if reduction in insomnia at mid- treatment (week 4), drives increased behavioural activation at the end of treatment (week 8), which in turn mediates the treatment effect on depression at follow-up (week 26)	ISI, BADS, PHQ-9	4-,8-, and 26weeks post- randomisation
Secondary	To compare the effect of SRT+TAU versus TAU on self-reported sleep and	Consensus Sleep Diary (CSD) -Sleep diary parameters:	8- and 26-weeks post- randomisation

	daily activation (over 1		
	week)	Sleep onset latency (SOL); Wake-time After Sleep Onset (WASO); Sleep Efficiency (SE); Total Sleep Time (TST); Sleep Quality (SQ); Time in Bed (TIB); Time to bed (TTB); Time out of Bed (TOB) -Level of daily activation computed from evening component of sleep diary	
Secondary	To compare the effect of SRT+TAU versus TAU on psychological well-being	Warwick-Edinburgh Mental Wellbeing Scale (WEMWBS)	8- and 26-weeks post- randomisation
Secondary	To compare the effect of SRT+TAU versus TAU on cognitive complaints	British Columbia Cognitive Complaints Inventory (BC-CCI)	8- and 26-weeks post- randomisation
Secondary	To compare the effect of SRT+TAU versus TAU on pre-defined adverse events	Suicidal ideation (PHQ9 item) and accidents (bespoke questionnaire)	4, 8 and 26- weeks post- randomisation
Tertiary	To compare the effect of SRT+TAU versus TAU on daytime activity levels and light exposure (1 week)	Gross and threshold levels of activity and light exposure quantified from actigraphy and measures of their phase	8- and 26-weeks post- randomisation

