8.3. Exclusion Criteria

The participant may not enter the trial if ANY of the following apply:

- Female participant who is pregnant or planning pregnancy during the course of the trial.
- Additional sleep disorder diagnosis OR "positive" on screening questionnaire (e.g., OSA, RLS)
- Dementia or mild cognitive impairment (MCI)
- Alcohol or substance-use dependent
- Epilepsy
- Psychosis (schizophrenia, bipolar disorder)
- Currently or recently received in-patient psychiatric treatment within the past 2 months
- Current suicidal ideation with intent OR attempted suicide within past 2 months
- Currently receiving cancer treatment OR planned major surgery during treatment phase
- Night, evening, early morning or rotating shift work
- Currently receiving psychological treatment for insomnia from a health professional or taking part in an online treatment programme for insomnia
- Previously received sleep restriction therapy from a health professional
- Life expectancy of <1 year
- Another person in the household already participates in this trial
- Currently taking part in another clinical trial which could affect outcomes in RESTED
- Recruiting clinician deems not suitable for the trial

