10. SAFETY REPORTING

10.1. Serious Adverse Event Definition

A serious adverse event (SAE) is any untoward medical occurrence that:

- results in death
- is life-threatening
- requires inpatient hospitalisation or prolongation of existing hospitalisation
- results in persistent or significant disability/incapacity
- Consists of a congenital anomaly or birth defect.

All participants, and the research nurses facilitating SRT, will be prompted to self-report SAEs. Along with self-reporting of SAEs, we will also ask participants about unplanned hospitalisations (as opposed to elective procedures or planned admissions for treatment) as part of the assessments at 4, 8, and 26 weeks, and follow-up participants who report being hospitalised.

We will record planned hospital admissions at baseline and when they occur, these will not be counted as SAEs. SAEs will be assessed for severity, seriousness, and relatedness to study procedures by a medically qualified member of the team. SAEs will be reported and followed up from date of randomisation until either the date of trial withdrawal or 26-week follow-up completion, whichever is earlier. Any SAEs that are continuing at trial withdrawal or 26-week follow-up completion will be marked as "Continuing" at the end of the study.

Other adverse events that require medical intervention may also be considered a serious adverse event when, based upon appropriate medical judgement, the event may jeopardise the participant and may require medical or surgical intervention to prevent one of the outcomes listed above.

NOTE: The term "life-threatening" in the definition of "serious" refers to an event in which the participant was at risk of death at the time of the event; it does not refer to an event which hypothetically might have caused death if it were more severe.

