10.3. Other Adverse Events

We will record incidences of falls, accidents (road-traffic accidents and work-related injuries), near miss driving incidents, and falling asleep while driving alongside outcomes at baseline, 4-, 8-, and 26-weeks post-randomisation. We will also assess proportion of each group showing an increase in suicidal ideation using item 9 from the PHQ9. As above, these outcomes will be assessed at baseline, 4-, 8-, and 26-weeks post-randomisation.

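### Suicide attempt and self-harm are not pre-defined safety outcomes and are not specifically asked about after randomisation; events without admission depend on SAE self-report and a seriousness judgement, with an extra reporting source in the SRT arm only

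*Protocol*

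**What the plan says.** **Safety outcomes after randomisation.** Section 9.8 gives them as "Falls, accidents (road-traffic and work-related), near-miss driving incidents, and falling asleep while driving; and suicidal ideation", with ideation taken from PHQ-9 item 9. Table 4 (section 6) shortens this to "Suicidal ideation (PHQ9 item) and accidents (bespoke questionnaire", compared at 4, 8 and 26 weeks, and the synopsis has the same row. Table 7 carries a similar list for baseline. Section 10.3 repeats the events ("We will record incidences of falls, accidents (road-traffic accidents and work-related injuries), near miss driving incidents, and falling asleep while driving") and states the suicide-related comparison as the "proportion of each group showing an increase in suicidal ideation using item 9 from the PHQ9".

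**Entry.** Section 8.3 excludes "Current suicidal ideation with intent OR attempted suicide within past 2 months", and Table 6 assesses recent attempt and current ideation with intent using the C-SSRS.

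**Serious adverse events.** Section 10.1 prompts all participants, and the nurses delivering SRT, to report SAEs. In addition, at 4, 8 and 26 weeks, "we will also ask participants about unplanned hospitalisations". The SAE criteria list death, life-threatening events and persistent disability separately from hospitalisation. A further clause allows other events needing medical intervention to be classed as serious on medical judgement. Section 11.2 compares the numbers of participants with SAEs between groups by chi-square or Fisher's exact test.

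**Nurse contact.** Section 9.4 states that the treating nurses interact only with participants in the experimental arm.

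**The concern.** Everyone enrolled has major depression, and the background section cites evidence that a poor night's sleep predicts more severe suicidal thoughts the next day in people with depression. The intervention restricts time in bed. Suicide-related safety is therefore a question that readers will put to this trial.

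The protocol separates thoughts from acts when deciding who may enter, but after randomisation it pre-defines an outcome only for thoughts. An increase on item 9 does not show whether anyone acted. If acts are not asked about by name, a report of no difference in suicidal ideation could be read as covering behaviour that was recorded only in part, and not in the same way in each arm.

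The gap is in data collection. A statistical analysis plan can choose how to tabulate what was recorded, but it cannot recover an answer to a question that nobody asked.

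**Working it through.** The point rests on no figure in the protocol, so the check sets the sections side by side.

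**1. Is an attempt or self-harm named anywhere as a safety outcome?** Five places list the pre-defined adverse events: the synopsis, Table 4, Table 7, section 9.8 and section 10.3. None names either. The omission is consistent and not a slip in one table.

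**2. Is there a follow-up instrument that would capture it?** The C-SSRS appears only at stage 2 of screening. The follow-up instruments in Table 8 and the schedule in Appendix B contain the PHQ-9 and an adverse-event entry, and no other suicide-related instrument. The accident items concern road traffic, work and driving, and would not naturally elicit a deliberate act.

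**3. By what route could each kind of event reach a between-arm comparison?**

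| Event | Route in the protocol | Comparison reached |
|---|---|---|
| Attempt with unplanned admission | Asked directly at 4, 8 and 26 weeks; also the SAE prompt | All SAEs pooled |
| Fatal, life-threatening or disabling attempt without admission | SAE reporting; meets a listed criterion | All SAEs pooled, if reported |
| Attempt or self-harm needing medical intervention, not admitted | SAE self-report, then a judgement that it may count as serious | All SAEs pooled, if reported and judged serious |
| Attempt or self-harm meeting no SAE criterion | None | None |

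The first row has a structured question. The second and third rest on a general prompt, and the third also on a discretionary classification. In the last row the event itself is not counted; only a rise on item 9 at a scheduled visit could reflect it, and that measures ideation. In no row is a separate count of attempts or self-harm by arm planned.

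**4. Is reporting the same in both arms?** All participants receive the SAE prompt. Section 10.1 adds the SRT nurses as a second prompted source, and section 9.4 confines those nurses to the SRT arm. Up to six nurse sessions per SRT participant therefore offer an occasion for disclosure that TAU participants lack. The likely direction is fuller reporting under SRT. That could make SRT look worse than it is on reported events, or complicate the reading of any difference.

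**5. Can the number of events affected be derived?** No. The protocol gives no rate of attempts or self-harm, no proportion admitted and no estimate of how completely the SAE prompt works. A count would have to be assumed, and none is offered here.

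**The case against.** A reader might infer that hospitalisation is the only event asked about directly, and that an attempt without admission therefore enters no safety comparison. The protocol supports neither inference. Section 10.3 also records falls, accidents, near misses and falling asleep while driving at each follow-up. Section 10.1 prompts every participant to report SAEs, so the report is prompted and not purely spontaneous, and the period runs from randomisation to withdrawal or completion of the 26-week follow-up. An attempt without admission that is life-threatening, or that needs medical intervention and is judged serious, is an SAE and counts in the section 11.2 comparison.

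The protocol also has protections. People with current ideation with intent, a recent attempt or recent psychiatric in-patient care are excluded. Consent lets the team contact the practice about health concerns at any point, and a data monitoring committee reviews safety. These lower the expected number of events and help protect individuals. They do not produce a count by arm.

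The bespoke adverse-event questionnaire is not shown and could already contain such a question. If so, the remaining defect is that the sections describing its content do not say so. It is also fair that the protocol does not contradict itself here: naming the outcome improves ascertainment and does not correct an error. What stands is the gap for events that meet no SAE criterion or go unreported despite the prompt, the absence of a separate count, and the additional reporting source in one arm.

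**Conclusion.** The concern holds in a bounded form. Suicide attempt and self-harm are absent from all five lists of pre-defined adverse events, and no specific question about them is stated for any of the three follow-up assessments. Admitted events, and non-admitted events that are reported and meet or are judged to meet an SAE criterion, are counted, but only within the pooled SAE total. Other events are not counted, and reporting opportunities favour the SRT arm.

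This does not bear on the primary analysis or the sample size. It limits what the trial can say about suicide-related safety. The conclusion assumes that the adverse-event questionnaire contains what the protocol says it contains. With 250 participants and the exclusions in section 8.3, events are likely to be few, so the value of the change lies in complete and even recording and not in a powered comparison. The change is worth making because it is cheap and the information cannot be recovered later.

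**What to change.** - Add one yes/no item to the existing adverse-event questionnaire at weeks 4, 8 and 26, asking about any suicide attempt or self-harm since the last assessment. Word and administer it identically in both arms.
- Name it among the pre-defined adverse events in Table 4, section 9.8 and section 10.3, and align the synopsis row.
- Send each 'yes' to the medically qualified team member already provided for in section 10.1 for the seriousness assessment.
- Report the number of participants with at least one event by randomised arm, descriptively, beside the item 9 result. Show separately any events known only through a nurse report, so that the extra source in the SRT arm is visible.
- If the questionnaire already asks this, state it in those sections; no new data collection is then needed.

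**Cost.** One added question and a short amendment. The question is sensitive, and follow-up questionnaires can be completed online or on paper, so answers need someone to review them; that is the main burden. If follow-up has already begun, visits before the amendment will lack the item and should be reported as not asked. Events will be few, and the result should not be presented as a test. Eligibility, treatment and sample size are unaffected.
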